5.4 Replacement of Subjects

Should a subject discontinue study treatment before receiving 6 cycles for reasons other than progression, another subject may be added to that study arm for full analysis.

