4.1.3 Safety Review Committee (SRC)

An SRC comprised of the Medical Monitor, enrolling PIs, and Sponsor representatives will hold periodic teleconferences to evaluate the safety and treatment status of all subjects available during the Safety Run-in (Part 1) at several stages:

- after 6 subjects Arm A have completed the first cycle,
- after 3 subjects in Arm C have completed the first cycle,
- at any other time as needed following random assignment in Part 2.

The safety run-in of Arm C (n=3) will occur with a 1-week interval between dosing of subjects and an SRC will convene after all subjects have received 1 cycle of therapy. The SRC has the authority to recommend dose or regimen modifications for safety concerns.

A written summary documenting the results and recommendations of each review will be provided to the investigator(s) and maintained on file with the Sponsor. Additional sub-investigators and personnel may participate in reviews, as appropriate.

Following a treatment arm review, the SRC may recommend proceeding with enrolling additional subjects in the current treatment arm or not enrolling any additional subjects.

While the SRC is expected to reach a consensus opinion regarding any premature discontinuation or significant modification of the study, the Sponsor may independently stop the study at any time.

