4.1.5 Treatment Arm Expansion Procedure

Should a subject discontinue study treatment before receiving 6 cycles for reasons other than progression, another subject may be added to the treatment arm to allow for full analysis. Response evaluation and criteria for futility are described in [Section 9 Statistical Methods](#).

Subject enrollment and expansion of treatment Arms A and C will proceed according to a standard Simon 2-stage design ([Table 1](#)). An alternate dose level of palifosfamide and/or INXN-1001 may be explored after review of all available safety and activity data, and will be communicated by an administrative letter and enacted upon issuance.

Table 1 Study Design (see Protocol Synopsis)

Part	Treatment Arm	Intervention (21-day cycle)
1 Safety Run-in	A	Ad-RTS-hIL-12 monotherapy (n=6) [INXN-1001 (140 mg daily) + INXN-2001 [REDACTED] [REDACTED] [REDACTED]
	C	Combination therapy; n=3 [INXN-1001 (140 mg daily) + INXN-2001 [REDACTED] [REDACTED] [REDACTED] + palifosfamide (120 mg/m ²)]
2 Randomization	A	Ad-RTS-hIL-12 monotherapy [INXN-1001 (140 mg daily) + INXN-2001 [REDACTED] [REDACTED] [REDACTED]
	C	Combination therapy [INXN-1001 (140 mg daily) + INXN-2001 [REDACTED] [REDACTED] [REDACTED] + palifosfamide (120 mg/m ²)]

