5.3 Withdrawal of Subjects from Study Treatment and/or Study

The investigator and/or the subject have the right to terminate the subject's participation in the study at any time. Subjects who discontinue study drug should complete the Post-Treatment Safety Assessment visit.

A subject **may** withdraw (or be withdrawn) from the study treatment prematurely for any of the following reasons:

- PI determines further participation is not in subject's best interest.
- Clinically significant disease progression

NOTE: In the absence of rapid clinical deterioration, disease progression should be confirmed by a repeat, consecutive assessment no less than 4 weeks from the date first documented to ensure that more slowly declining total tumor burden in response to therapy is not missed.

A subject **MUST** be withdrawn in the event of any of the following:

- Withdrawal of informed consent.
Note: Any subject who wishes to withdraw from the study treatment may do so but will be counseled that follow-up for the effects of immunotherapy is strongly recommended.
- Any treatment-related AE meeting withdrawal criteria.
- Substantial noncompliance with the requirements of the study.
- Subjects with a confirmed positive pregnancy test.
- Any intercurrent illness that would, in the judgement of the investigator, affect assessments of clinical status to a significant degree and require discontinuation of protocol therapy.

Every effort should be made to follow subjects who withdraw from study treatment with ongoing treatment-related AEs in order to determine the outcome of the event.

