8.1 Determination of Sample Size

In view of up to 3 novel investigational drugs being tested in this study, the sponsor has incorporated a Safety Run-in (Part 1) to evaluate safety for each study arm before fully enrolling all subjects required in Stage 1 of Part 2 for each study arm (for details please see [Section 5.1.1](#)).

The sample size of Part 2 is determined based on a Simon 2-stage design for each study arm. For Ad-RTS-hIL-12 monotherapy (Arm A) with 13 subjects evaluated in Stage 1 and an additional 20 subjects in Stage 2 if applicable, it will provide 80% power at 1-sided 5% significance level to differentiate 35% targeted proportion of subjects who survive progression-free at week 16 from a proportion of no interest of 15%. If ≥ 3 of 13 subjects survived progression-free at week 16 in Stage 1, 20 additional subjects will be evaluated in Stage 2.

For the Ad-RTS-hIL-12 + palifosfamide combination (Arm C), with 12 subjects evaluated in Stage 1 and an additional 14 subjects evaluated in Stage 2, it will provide 80% power at 1-sided 5% significance level to differentiate 65% targeted proportion of subjects who survive progression-free at week 16 from a proportion of no interest of 40%. If ≥ 6 of 12 subjects survived progression-free at week 16 in Stage 1, 14 additional subjects will be evaluated in Stage 2.

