8.4 Study Endpoints

8.4.1 Primary Efficacy Endpoint

The primary efficacy endpoint is the 16-week PFS rate, calculated as the number of subjects who had not progressed or died prior to 16 weeks from the date of their first dose, divided by the number of subjects in the study arm. Subjects who neither progressed nor died, but had their last tumor assessment prior to 16 weeks, will not be categorized as progression-free and will not be included in the numerator. Progressive disease (PD) will be determined by mRECIST v1.1 (please refer to [Appendix 4](#)).

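### The replacement rule in 4.1.5 and 5.4 is not reconciled with the fixed stage counts, so replacing subjects who stop for toxicity makes a go decision easier and leaves the 1-sided 5% level unprotected

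*Protocol*

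**What the plan says.** **Replacement.** Protocol 5.4 (Replacement of Subjects): "Should a subject discontinue study treatment before receiving 6 cycles for reasons other than progression, another subject may be added". Section 4.1.5 repeats the rule and gives its purpose: "another subject may be added to the treatment arm to allow for full analysis". Neither section excludes toxicity or death, limits the rule to Part 1 or Part 2, or says who decides and when. Section 5.3 lists among the mandatory reasons for withdrawal "Any treatment-related AE meeting withdrawal criteria".

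**Decision rules.** The synopsis and 8.1 use fixed counts. Arm A needs at least 1 of the first 6 (synopsis), 3 of 13, then 9 of 33. Arm C needs at least 6 of 12, then 15 of 26. For Arm A, 8.1 makes this claim: "it will provide 80% power at 1-sided 5% significance level to differentiate 35% targeted proportion of subjects". The no-interest rate there is 15%. Arm C has the same level and power for 65% against 40%.

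**Endpoint.** Section 8.4.1 counts deaths before 16 weeks as failures. An event-free subject without a late enough scan is not a success either; the wording is: "had their last tumor assessment prior to 16 weeks, will not be categorized as progression-free and will not be included in the numerator". The divisor is all subjects in the arm. Section 8.6.4, however, analyses efficacy in the Efficacy Evaluable Population, which 8.3 limits to dosed subjects with a response evaluation after screening. The first scheduled evaluation is at week 12 (6.4.3).

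**Run-in.** Section 4.1.3 sets the Arm C review "after 3 subjects in Arm C have completed the first cycle", and the Arm A review likewise after 6. The same section says the committee evaluates all subjects available in the run-in.

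**SAP.** The SAP supplied describes a single-arm, one-cycle study. It has no replacement rule and no stage counts.

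**The concern.** A two-stage rule with fixed cutoffs has its stated error rate only if each place holds one unselected subject. Here a subject whom 8.4.1 scores as a failure can lead to another subject being enrolled, and the text leaves two ways to count the newcomer:

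- The newcomer takes the place. The failure leaves the count.
- Both are counted. The number of subjects grows while the required number of successes stays the same.

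Either way the cutoff is easier to reach. Keeping the failure in the 8.4.1 divisor does not prevent this, because the rules are written as success counts and not as rates. The Efficacy Evaluable restriction works in the same direction, since a dosed subject who stops early and is never scanned after screening leaves the analysis.

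Replacement is optional and the study is open-label, so the choice can be made with the subject's outcome known. At stake is the primary efficacy decision in each arm, and in particular the comparison of the cytotoxic combination with its 40% no-interest rate.

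**Working it through.** **Inputs.** Cutoffs, no-interest rates p0 (15%, 40%) and targets p1 (35%, 65%) come from the synopsis and 8.1. The anticipated maximum of 62 comes from the synopsis. The replaced share q is assumed, because the documents give none. It covers only subjects who stop for a non-progression reason, fail 8.4.1 and are replaced. A stopper scanned progression-free at week 16 is a success and is not in q.

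**Step 1: reproduce the design.**

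P(go) = Σ over x ≥ r1 of Bin(x; n1, p) × P[Bin(n − n1, p) ≥ r − x]

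- Arm A (3/13, 9/33): 4.1% at p = 0.15 and 80.8% at p = 0.35. With the 1-of-6 look: 3.9% and 78.0%.
- Arm C (6/12, 15/26): 4.7% at p = 0.40 and 80.9% at p = 0.65.

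The two-stage figures agree with the stated 5% and 80%.

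**Step 2: the newcomer takes the place, no limit on number.** Hold the success rate among all dosed subjects at p0. Each enrolled subject is a success with chance p0, a replaceable failure with chance q, or another failure. Once replaceable failures are removed and refilled, the success chance per place is p* = p0/(1 − q). At q = 20%, for example, 0.15/0.80 = 0.1875 and 0.40/0.80 = 0.50. Putting p* into Step 1:

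| q | Arm A | Arm A with 1-of-6 look | Arm C |
|---|---|---|---|
| 0 | 4.1% | 3.9% | 4.7% |
| 3% | 4.9% | 4.6% | 6.1% |
| 10% | 7.2% | 6.8% | 11.2% |
| 20% | 12.8% | 12.1% | 25.7% |

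**Step 3: the newcomer is counted as well, cutoffs unchanged.** With 3 subjects added to an arm, 1 of them in Stage 1, the counts become 3/14 and 9/36 (Arm A) or 6/13 and 15/29 (Arm C). P(go) at p0 is 6.6% in Arm A and 11.9% in Arm C. A single subject added in Stage 2 of Arm C (15 of 27) already gives 6.4%.

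**Step 4: limit from the stated sample size.** Both arms in full need 33 + 26 = 59 subjects, so 62 − 59 = 3 places are spare. Unlimited replacement at q = 20% would need 59/0.80 ≈ 74 subjects, and at q = 10% 59/0.90 ≈ 66. Now allow at most 3 replacements, all in one arm. Let f(i, s, k) be the chance of go with i places filled, s successes and k replacements left:

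f(i, s, k) = p0·f(i+1, s+1, k) + (1 − p0 − q)·f(i+1, s, k) + q·f(i, s, k−1)

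When k = 0 the last term is q·f(i+1, s, 0). f is 0 when a look is missed and 1 when the last look is passed. At q = 20% this gives 7.0% in Arm A (without the 1-of-6 look) or 12.5% in Arm C.

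**The case against.** Most of the case on the other side narrows the point without removing it.

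- **Safety.** A reader might infer that replacement hides intolerance from the run-in. The documents do not support that: the Safety Population keeps every dosed subject (8.3), discontinuations due to adverse events are listed (8.6.3), and the committee reviews all available subjects (4.1.3). What stands is that the review is triggered by 6 and 3 subjects completing cycle 1, and that number can be reached through replacement.
- **Stopping is not failing.** Section 6.4.3 schedules week 12, 16 and 24 assessments for all subjects, and 9.4 continues follow-up after discontinuation. If half of all stoppers are progression-free at week 16, a 20% stopping rate means q = 10%.
- **Death.** Section 8.6.4.2 treats death without reported progression as progression. That defines the PFS endpoint, not replacement, but it makes the reading of 5.4 for deaths arguable. Toxicity stops are not affected.
- **Sample size.** The maximum of 62 leaves little room if both arms fill. It is an anticipated number, though, and places are freed if one arm stops early.
- **The decision is not mechanical.** The synopsis speaks of considering a confirmatory trial and bases futility on primary and secondary endpoints, and 8.6.4.1 reports an exact confidence interval. This softens the consequence, but 8.1 still claims a 5% level for these cutoffs.

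**Conclusion.** The point holds for efficacy. Sections 4.1.5 and 5.4, the populations in 8.3 and 8.6.4, the endpoint in 8.4.1 and the stage counts are not reconciled, and either reading of replacement raises the chance of go at the no-interest rate.

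The size depends on q, on whether the rule is used and on how many replacements are possible. A reader might infer that the 5% level is lost outright. That is too strong: Arm A is still at 4.9% when q = 3%. Arm C has less margin and reaches 6.1% at the same q. The 25.7% for Arm C needs q = 20% and enrolment beyond 62 if both arms fill; with 3 replacements it is about 12.5%. The supported conclusion is that the level is not protected, more so in Arm C.

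**What to change.** - **5.4 and 4.1.5:** for the efficacy stages, only subjects never dosed may be replaced. Every dosed subject keeps the place, in enrolment order, in the 13/33 and 12/26 counts and is scored by 8.4.1.
- **8.3 and 8.6.4:** the stage decisions and the primary 16-week PFS rate use all dosed subjects in the arm. The Efficacy Evaluable analysis becomes supportive. Without this change, early stoppers never scanned after screening would still drop out.
- **4.1.3:** reconcile the cycle-1-completion trigger with the all-available scope by stating that the run-in review covers every dosed run-in subject, including those who left in cycle 1.

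This keeps the two-stage error rates of Step 1 (4.1% and 80.8%; 4.7% and 80.9%), with the no-interest and target rates read as rates among all dosed subjects. It adds no patients. The cost is that an occasional subject lost for an unrelated reason counts as a failure, which slightly lowers the observed rate. Section 8.4.1 already accepts this.

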5.5 Premature Termination of Study/Closure of Center

The sponsor has the right to close the study at any time, although this should occur only after mutual consultation between the sponsor and the investigators. The institutional review board (IRB)/independent ethics committee (IEC) must be informed. Should the study/center be

closed prematurely, all study materials (completed, partially completed, and blank case report forms, study medication, etc.) must be stored or disposed of according to the sponsor's instructions. Events that may trigger premature termination of the study or closure of a center include, but are not limited to, a new toxicity finding, results of any interim analysis, noncompliance with the protocol, change in development plans for the study drug, slow recruitment, or poor-quality data.

6. TREATMENT PROCEDURES

6.1 Screening

PIs at each site are responsible for maintaining a record of all subjects screened, including both those who enter the study and those who are excluded.

6.1.1 Informed Consent

Each potential subject must sign a written, informed consent form prior to performing any study specific screening procedure.

6.1.2 Inclusion and Exclusion Criteria

Inclusion and exclusion criteria will be reviewed for each potential subject and documented in the case report form (CRF).

6.1.3 Registration/Randomization of Subjects

Centralized registration/randomization of subjects will be completed according to a process defined by the sponsor (see [Section 5.1.4](#)). Each subject will be assigned a unique identification number. Once assigned, a subject's identification number will not be reused.

6.2 Study Drugs

6.2.1 Accountability and Dispensation

The PI must maintain accurate records accounting for the receipt and dispensation of the study drugs.

The investigational materials are to be prescribed only by the PI or the sub-investigators named on the United States Food and Drug Administration (US FDA) Form 1572, and may only be dispensed by authorized personnel at the institution(s) listed therein.

Under no circumstances will the PI allow the investigational drug(s) to be used other than as directed by the protocol.

6.2.2 Handling and Storage

Study drugs must be stored in a restricted access area under the storage conditions indicated in the Investigator's Brochure(s) or Pharmacy Manual.

All necessary precautions while handling potentially toxic compounds must be strictly followed.

6.2.3 Treatment Regimen

A combination of up to 3 investigational medications will be evaluated for safety, tolerability, efficacy, and biological effects in this trial. The small molecule INXN-1001 will be administered as oral capsules (once daily doses on Days 1-7) in combination with an IT injection of INXN-2001 (on Day 1 of each cycle). For each 21-day treatment cycle, INXN-2001 dosing will occur 3 hours \pm 30 minutes after the first dose of INXN-1001. INXN-2001 will be given as IT injections of approximately [REDACTED] 1 mL per treatment.

Following Cycle 1, if no accessible lesion for INXN-2001 injection is present (eg, due to complete resolution), then INXN-2001 should be injected into an alternate lesion or a draining, pathologic lymph node of a previously accessible lesion. A pathologic lymph node must be defined as a lesion per mRECIST ([Appendix 4](#)). The injections will be administered on the first day of each cycle throughout the study. Subjects must be adequately hydrated on each day of study drug administration. Subjects must be instructed to maintain good oral hydration on and between dosing days.

[REDACTED]

[REDACTED]

[figure not shown]
[REDACTED]

For treatment Arm C Combination

Therapy (Ad-RTS-hIL-12 + palifosfamide), palifosfamide will be administered following administration of INXN-1001 as a 30-minute IV infusion, and on Day 1 of each cycle the infusion should complete before injection with INXN-2001.

Palifosfamide will be administered intravenously at a dose of 120 mg/m²/day as a 30-minute infusion on Days 1, 2, and 3 of a 21-day cycle for up to 6 cycles.

The temporal sequence of the treatment regimens for study Arms A and C are shown in [Figure 4](#). For subjects enrolled in Arm C Ad-RTS-hIL-12 + Palifosfamide Combination Therapy, the sequence of regimens A + palifosfamide will be followed concurrently as shown below.

Figure 4. Study Arm Treatment Regimens**6.2.4 Preparation and Administration of Study Drug**

Please refer to the Pharmacy Manual for additional information.

6.2.4.1 Preparation and Administration of INXN-1001

INXN-1001 will be provided by the Sponsor as capsules.

INXN-1001 capsules will be dispensed for subject oral dosing by the site pharmacy. The site must instruct the subject to take each dose in a fed state (within approximately 30 minutes after the start of a normal meal).

6.2.4.2 Monitoring of Subject Adherence and Managing Missed INXN-1001 Doses

The first daily dose of INXN-1001 at each treatment cycle is expected to be administered to the subject at the clinical site, under careful medical supervision by the clinic staff to ensure that the subject does not have difficulty with the size or quantity of capsules to be administered. Thereafter, subjects may be allowed to self-administer the remaining 6 doses at approximately the same time and in the same relationship to meals as administered at the clinical site on Day 1 of the treatment cycle. Subjects are to be instructed to take all of the capsules in the same way for each of the remaining treatment period, and will be reminded to take their dose via a phone call when they will not have a clinic visit.

Subjects should be instructed not to make up for missed doses.

Subjects will also be instructed to bring the treatment container(s) back with all remaining capsules at the next visit, to provide an assessment of the degree of adherence. All subjects will be queried about dose schedule adherence and reasons for missed doses.

6.2.4.3 Preparation and Administration of INXN-2001

INXN-2001 will be supplied by the Sponsor as single-dose vials. Information regarding the preparation of the INXN-2001 dose will be provided in the Pharmacy Manual.

INXN-2001 [REDACTED] will be administered as an IT injection 3 hours (\pm 30 minutes) after oral INXN-1001 dosing on Day 1 of each cycle. INXN-2001 should be injected into a different lesion at each cycle. If only 3 accessible lesions are present, the injections will be done in sequential rotation between 2 lesions. If only 2 accessible lesions are present, then all injections will be into a single lesion. If only 2 accessible lesions are present at screening, and the single injected lesion can no longer support the injection volume at subsequent cycles, then the Medical Monitor should be contacted for determination of a path forward. Lesions displaying signs of localized infection should not be injected.

Note: In the absence of the availability of radiographically-guided injections, one accessible lesion will not be injected since that lesion will be used to evaluate the systemic effect of INXN-2001.

The INXN-2001 IT administration should be delivered by multiple injections with a fine needle (no finer than 27 gauge) directly into each quadrant of the lesion or pathologic lymph node to reach all aspects of the entire lesion. Attention must be paid to adequately infiltrate the circumference of the tumor margins.

Should the tumor selected for injection not support the entire INXN-2001 injection volume (approximately 1 cc), another tumor should be injected with the remaining volume to ensure that all subjects receive approximately [REDACTED]. If another tumor is not available, then the remaining volume should be injected into a draining, pathologic lymph node of the injected tumor. At any cycle, if no accessible lesion for INXN-2001 injection is present (eg, due to complete resolution), then INXN-2001 should be injected into a draining, pathologic lymph node of a previously accessible lesion. A pathologic lymph node must be defined as a lesion per mRECIST ([Appendix 4](#)).

NOTE:

- All subjects receiving INXN-2001 must be adequately hydrated with approximately 2000 mL per 24 hours of oral electrolyte solution for 72 hours during Cycles 1 and 2. Subjects must be instructed to maintain good oral hydration on and between dosing days.

Each subject will be carefully monitored for possible local reactions at the injection site and/or hypersensitivity reactions, for at least 2 hours following the INXN-2001 injection. The subject should be instructed to call the clinical site if any such reactions develop or do not resolve within 24 to 48 hours.

6.2.4.4 Preparation and Administration of Palifosfamide

Palifosfamide should be administered IV at a dose of 120 mg/m²/day, as an approximate 30-minute infusion on Days 1, 2, and 3 of a 28-day cycle, for up to 6 cycles. Palifosfamide is supplied in single-use glass vials each containing 350 mg of active product. Each vial is to be reconstituted with sodium chloride injection, USP, to a final concentration of 50 mg/mL and appropriate dose transferred into a 250 mL 0.9% sodium chloride IV infusion bag.

Note: Total cumulative time from reconstitution in vial through completed dose administration should not exceed 2.5 hours (150 minutes).

Information regarding the preparation of the palifosfamide dose will be provided in the Pharmacy Manual. The dose (mg) of palifosfamide should be calculated based on the subject's actual body weight as measured on Day 1 of each cycle. Body surface area (BSA) may be calculated as per the standard practice at each investigative center; however, the same formula should be used throughout the study when calculating a subject's BSA. The palifosfamide dose must be prepared as described in the Pharmacy Manual, and administered within permitted time window allowed for reconstitution in vial, dilution in the IV infusion bag, and through completion of the IV infusion.

NOTE:

- All subjects receiving palifosfamide must be adequately hydrated with at least 500 mL of fluids (oral or IV as appropriate), in addition to the infusion administered, on each day of palifosfamide dosing. Subjects should be instructed to maintain good oral hydration on and between dosing days.
- Electrolytes and hematologic toxicity need to be carefully monitored during clinical studies with palifosfamide.

Study treatment should be administered according to the planned 21-day treatment cycle, with treatment delays allowed for study-drug related toxicity as described in [Section 7.2.5](#). If the Day 1 visit for a re-treatment cycle is delayed for other reasons (eg, due to inclement weather), then the visit should be rescheduled to occur as soon as possible. If any non-prolonged delay for other reasons is to occur, the Medical Monitor should be consulted.

A missed Day 2 or Day 3 study drug administration may be rescheduled to Day 4 of the same treatment cycle. If both Day 2 and Day 3 are missed, then only a single day may be rescheduled to Day 4 and the other will be skipped. In either case, the total duration of the treatment cycle should remain 21 ± 1 day by shortening the rest interval by 1 day. If the missed dose cannot be administered on Day 4, then it must be skipped and the subject should continue on protocol and take the next dose as originally planned.

